### The microbiome of the pouch

It has previously been shown that up to 60-80% of pouch microbiota cannot be cultured (30), and this has complicated microbiome studies greatly. Culturing bacteria of the gastrointestinal tract greatly favors aerobic bacteria, which can result in misleading findings. The development of 16S rRNA (16S ribosomal ribonucleic acid) sequencing has revolutionized microbial diagnostics. It allows detection and quantification of non-culturable as well as slow-growing bacteria in both a clinical and research setting. However, it does not assess the viability of the detected bacteria.

Studies have shown considerable differences between bacteria found in the pouch lumen and feces, and bacteria adherent to the mucosa (31,32). Especially the bacteria found in the mucosa are thought to be involved in the pathogenesis of IBD and pouchitis because they are in close contact with the host and the immune system (31,33).

Tissue biopsies from the pouch mucosa will be analyzed in our study for change in bacterial composition with 16S rRNA sequencing.

It is still unclear which bacteria are responsible for the development of pouchitis, but several bacteria have been associated with inflammation whereas others usually found in healthy pouches disappear or are reduced in number in pouchitis. In general, it is thought that a lower bacterial diversity leads to inflammation. Enterobacteriaceae, streptococci, Bacteroidetes, and enterococci are thought to be involved in the maintaining of gut homeostasis, and low levels of these bacteria favor the development of pouchitis (34). As opposed to this, a higher incidence of proteobacteria and sulfate-reducing bacteria such as clostridia are found in the inflamed pouch (35–37).

Bacteria increased in pouchitis	Bacteria in healthy pouches or reduced in pouchitis
Proteobacteria Clostridia (especially C. perfringens ) Bacteroidaceae Roseburia Akkermansia Escherichia coli (AIEC) (38)	Bacteroidetes Faecalibacterium prausnitzii Veillonella Staphylococci Enterobacteriaceae Streptococci Enterococci Bifidobacteriaceae Eubacteriaceae Bacillaceae Moraxellaceae Burkolderaceae Corynebacteriaceae Sutterella
Inconclusive	
Lachnospiraceae Ruminococcus	

Fusobacterium
----------------------

Table 1: Overview of bacteria associated with pouchitis

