##### Secondary outcome measures

- Change in the pouchitis disease activity index (PDAI) – A decrease of 3 points or more will be determined as an improvement in PDAI from before application of the study drug to 7 days after application of the study drug
- Change in median WBC, CRP, creatinine and liver enzymes from before application of the study drug to 7 days after application of the study drug
- Change in microbial diversity in the pouch using 16S rRNA sequencing from before application of the study drug to 7 days after application of the study drug

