### Secondary outcome measures

- Change in the clinical, endoscopic or histological PDAI – A decrease of 3 points or more will be determined as an improvement in PDAI from before application of the study drug to 7 days after application of the study drug
- Change in median WBC, CRP, creatinine and liver enzymes from before application of the study drug to 7 days after application of the study drug
- Change in microbial diversity in the pouch using 16S rRNA sequencing from before application of the study drug to 7 days after application of the study drug
- Safety: Determine serious adverse reactions or adverse reactions from the application of GM-CSF, metronidazole and fosfomycin in the pouch as seen in Appendix 8.

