## 8. Statistical considerations

We plan to include 6 patients in the Phase I study to test tolerability, and 12 patients in the Phase II study to test effectiveness of the treatment. The trial will end with the last visit of the last patient (Day 37 of the last patient). This is a safety and clinical proof-of concept intervention study, and we are, to the best of our knowledge, the first group to look into local treatment with GM-CSF and antibiotics of biofilm in patients with pouchitis after IPAA for ulcerative colitis. We expect this number of patients to be sufficient to provide the necessary experience in implementing the technique and form a basis for future studies, including future sample size calculation. This is based on calculations on number of patients required to achieve statistical significance of paired before-and-after comparisons by non-parametric tests. To achieve statistical significance at 1% level in Phase II, 9 patients are needed. As there is a risk of patients withdrawing from the trial prematurely or not receiving all interventions, we aim to include 3 additional patients.

Our primary objective is to test for adverse events or reactions in Phase I and a significant change in PDAI in Phase II, defined by a decrease of 3 points. Differences pre- and post-treatment will be described by means and standard deviations, or median and range when appropriate, and will be analyzed by the appropriate statistical tests. All patients described in chapter 5 as 'Completed test persons' will be included in the statistical analysis.

Microbial diversity changes will be analyzed using PERMANOVA (permutational analysis of variance). Other secondary objectives like change in WBC and CRP will be analyzed using the appropriate statistical tests.

Data will be analyzed using non-parametric or parametric statistics depending on the distribution of the data. P-values  $\leq 0.05$  are considered significant. Correction for multiple comparisons will be performed if needed. Descriptive statistics will be used for baseline characteristics.

Missing data will be handled depending on the type of data missing. If missing data results in a patient not being able to be defined as a 'Completed test person' (Chapter 5), the patient is excluded from the trial and a new patient will be recruited. If individual results are missing (e.g. laboratory values), the last known values will be used for analysis.

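### PERMANOVA is the only analysis named for the change in microbial diversity; as usually applied it cannot show whether diversity rose or fell, and no within-patient blocking is stated for it

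*Protocol*

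**What the plan says.** Section 3 lists the same secondary outcome for Phase I and Phase II: "Change in microbial diversity in the pouch using 16S rRNA sequencing from before application of the study drug to 7 days after application". Section 8 assigns it a method: "Microbial diversity changes will be analyzed using PERMANOVA (permutational analysis of variance". This is the only outcome in Section 8 with a named test; for PDAI, WBC and CRP the choice of test is left open. No distance measure, model term or permutation scheme is given for PERMANOVA, and no diversity index is named anywhere in the protocol.

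Section 2, under the heading on the pouch microbiome, uses two different ideas. One is the rationale: "In general, it is thought that a lower bacterial diversity leads to inflammation". The other describes what will be done: "Tissue biopsies from the pouch mucosa will be analyzed in our study for change in bacterial composition with 16S rRNA sequencing".

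Section 8 also makes clear that the design is paired. On the number of patients it says: "This is based on calculations on number of patients required to achieve statistical significance of paired before-and-after comparisons by non-parametric tests".

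**The concern.** Two questions arise.

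- **What is tested.** Diversity in the sense of the Section 2 rationale belongs to a single sample and can be higher or lower. PERMANOVA on between-sample distances asks whether the before and after samples differ in composition. A significant result would not show whether diversity had recovered, and a real change in diversity could be reported without a direction.
- **How the pairs are handled.** Pouch communities can be expected to differ between patients. If labels are permuted across all samples, those differences enter the reference distribution and can hide a consistent within-patient change.

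The trial is meant to inform later studies. A false finding of no change, or a positive finding that cannot be interpreted, would carry over into their design.

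**Working it through.** **1. The plan's own figure, which shows the pairing.** Section 8 says "To achieve statistical significance at 1% level in Phase II, 9 patients are needed". With n pairs all changing in the same direction, the smallest two-sided p of a sign or signed-rank test is 2/2^n:

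- n = 7: 2/128 = 0.0156
- n = 8: 2/256 = 0.0078
- n = 9: 2/512 = 0.0039

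The 1% level is first reached at 8 pairs, so the stated 9 is close, and 9 + 3 = 12. This figure does not concern the microbiome. It shows only that the sample size was reasoned from paired data.

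**2. Composition against diversity.** Take four taxa with shares (.5, .3, .15, .05) before and (.05, .15, .3, .5) after.

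- Shannon, H = -Σ p ln p: .347 + .361 + .285 + .150 = 1.142 (from unrounded terms). After treatment the same four terms appear in another order, so H is again 1.142.
- Bray-Curtis for shares, Σ|difference|/2: (.45 + .15 + .15 + .45)/2 = 0.60.

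If patients shifted in this way, the distance-based test would see a large change while diversity had not changed at all.

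**3. Why unrestricted permutation is conservative.** The statistic is F = (SST - SSW)/(SSW/(N - 2)), with N = 2n samples in two groups. Every patient appears once in each group, so patient effects cancel in the observed before/after contrast. Unrestricted relabelling breaks that balance. For one taxon on the log scale with no effect, the variance of the difference in means is 2σw²/n as observed, but about 2(σb² + σw²)/n over free permutations. With σw = 0.5, the ratio σw²/(σb² + σw²) is:

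- σb = 0.5: 0.25/0.50 = 0.5
- σb = 1.0: 0.25/1.25 = 0.2
- σb = 1.5: 0.25/2.50 = 0.1

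**4. Size of the loss.** The protocol gives no variances, so all of these inputs are assumptions: Bray-Curtis distance, 40 taxa, log-scale within-patient SD 0.5, a shift of 0.8 in 10 taxa (alternating up and down), 5% level, 400 runs and 199 permutations. Power is shown as free / within-patient permutation:

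| Patients | Between-patient SD 0.5 | SD 1.0 | SD 1.5 |
|---|---|---|---|
| 6 | 22% / 62% | 0.2% / 48% | 0% / 42% |
| 9 | 50% / 94% | 0.5% / 86% | 0% / 73% |
| 12 | 73% / 99% | 2% / 96% | 0% / 91% |

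- With a shift of 0.5 and 12 patients: 13.5% / 73%, 0% / 57.5%, 0% / 43%.
- With no shift, across all three sample sizes: free permutation rejects 0-0.2%, within-patient permutation 2-7%. The Monte Carlo standard error at 5% is √(.05 × .95/400) = 1.1 points.
- A separate Bray-Curtis simulation at 12 patients gave 71%, 0% and 0% free against 99%, 96% and 83% within patient.
- A Euclidean version (30 features, a third shifted by 0.75 SD, between/within SD ratios 1, 1.5 and 2) gave 4%, 0% and 0% against 89%, 93% and 89%.

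**5. Is the remedy workable at these sizes?** Within-patient swaps give 2^n labellings, and swapping every pair returns the same F, so the smallest p is again 2/2^n: 2/64 = 0.031 at 6 patients, 0.0039 at 9 and 0.0005 at 12. The 0.05 level is attainable in both phases, by restricted PERMANOVA and by the signed-rank test.

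**The case against.** A reader might infer that the protocol has chosen an unpaired analysis. It has not. It says nothing on permutation, and the same section reasons from paired comparisons. Blocking and permutation settings are also often left to a statistical analysis plan, which is not available here. This stands: the power loss is conditional on how the test is run and is not a property of the plan as written.

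A reader might also infer that PERMANOVA does not test the stated outcome at all. That is too strong. Section 2 describes the biopsy analysis as a change in composition and tabulates taxa that are raised or reduced in pouchitis, which suits PERMANOVA. Diversity can mean between-sample diversity, and the method can be run on a single index with Euclidean distance. What remains is that two quantities share one word, no index is named, and the usual form of the only named test cannot answer the directional question in the rationale.

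Nor do the results support saying that the test would report no change whatever the drug does. With modest between-patient variation, free permutation kept 73% power at 12 patients.

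Finally, the outcome is secondary in a proof-of-concept trial that disclaims definitive efficacy answers. That limits the consequence, but the change costs very little.

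**Conclusion.** The point holds in a limited form and is worth correcting. The mismatch between test and outcome rests on the protocol's own text: it names one method for a change in diversity, and in usual practice that method assesses composition without direction. The pairing part is a gap in specification. If permutation were unrestricted, power at 12 patients would be roughly 0-73%, against 83-99% with within-patient permutation, and the loss grows with between-patient variation. Those ranges come from the Bray-Curtis simulations with assumed variances, at the 0.8 shift for the tabulated run. The size is therefore uncertain, but the direction was the same in every scenario with a true change. No primary outcome is affected.

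**What to change.** In Section 8, replace the single PERMANOVA sentence with two statements:

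1. Within-sample diversity, measured by one named index (for example Shannon), is compared before and after treatment with a paired Wilcoxon signed-rank test, and the direction and size of the change are reported.
2. Community composition is compared by PERMANOVA on a named distance, with permutations restricted within patient.

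Sections 2 and 3 should then use diversity and composition for these two quantities consistently. If a statistical analysis plan already sets the index and the permutation scheme, a cross-reference to it is enough.

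The cost is one extra secondary test per phase, to be counted under the multiple-comparison provision already in Section 8, and a permutation setting in the R code. No new samples, visits or patients are needed.

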#### A completed test person

A completed test person is defined as:

Phase I: a patient who received the therapeutic endoscopy, clinical examination and had pre-treatment blood samples drawn, and then came for a clinical appointment on day 7 with new blood samples drawn, clinical examination, and control endoscopy

Phase II: a patient who received the initial endoscopy, clinical examination and had pre-treatment blood samples drawn, and then received the enema daily for 7 days and came for a clinical appointment on day 14, when new blood samples were drawn, and clinical examination and control endoscopy performed

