#### Reasons for withdrawal

A patient will be discontinued from participation in the study

- if any clinical AE or AR (adverse event or reaction), laboratory abnormality, intercurrent illness, or other medical condition or situation occurs which suggests that continued participation in the study would not be in the best interest of the patient. This also concerns the necessity of initiating a particular drug treatment, e.g. antibiotics for infection or taking a 'rescue drug' for a medical condition, that interacts with the study drug
- when developing any of the exclusion criteria

Patients can voluntarily withdraw from participation in this study at any time as well as withdraw from receiving the study intervention for any reason. The patients will be informed of this right in accordance with the Helsinki Declaration.

The investigator can withdraw a patient if the investigator considers that the safety of the patient is compromised by the participation in the study. In that case, the investigator must inform the patient about the reason for withdrawal.

When patients withdraw from the study, reasons for withdrawal, if given, will be documented in the CRFs (Case report forms). The number of dropouts and withdrawals will be reported. No further data will be collected from the patients withdrawing from the study; however, the previously collected data will be part of the final data analysis unless the patient specifically requests all data to be deleted. Patients that have received the study medicine will be contacted by telephone two weeks after receiving the study medicine, to ensure patient wellbeing. This data after withdrawal from the study, will not be collected and is meant solely to ensure the safety of the patient.

In case of withdrawal due to AE or AR, safety data will be collected and the patient will be followed until given appropriate care under medical supervision or until symptoms of any AE or AR resolve or become stable.

Participants who discontinue early will be replaced. This concerns all patients that have not undergone the second endoscopy. In case of withdrawal due to a serious adverse event (SAE) or serious adverse reaction (SAR), continuity of inclusion will be discussed with the sponsor.

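### Section 8 in effect limits the Phase II PDAI result to completers and replaces the rest, so treated patients who stop early can be missing from it; sections 5 and 8 are not aligned on this

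*Protocol*

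**What the plan says.** Section 8 states: "All patients described in chapter 5 as 'Completed test persons' will be included in the statistical analysis". If missing data keep a patient from that status, "the patient is excluded from the trial and a new patient will be recruited". The next sentence deals with isolated gaps: "If individual results are missing (e.g. laboratory values), the last known values will be used for analysis". The Phase II number is 9 patients plus an allowance: "As there is a risk of patients withdrawing from the trial prematurely or not receiving all interventions, we aim to include 3 additional patients".

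Section 5 (A completed test person) defines the Phase II completer. The patient had the initial endoscopy, examination and bloods, "received the enema daily for 7 days", and attended on Day 14, "when new blood samples were drawn, and clinical examination and control endoscopy performed".

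Section 5 (Reasons for withdrawal) discontinues patients for adverse events or reactions, laboratory abnormalities or intercurrent illness that make staying in the study unwise. It adds: "This also concerns the necessity of initiating a particular drug treatment, e.g. antibiotics for infection", if the drug interacts with the study drug. A further ground is "when developing any of the exclusion criteria", and current antibiotic treatment is an exclusion criterion. After withdrawal, data collection ends, except for safety data when the cause was an adverse event or reaction.

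The same section keeps data already collected in the final analysis unless the patient asks for deletion. It describes replacement for patients who have not had the second endoscopy, and it promises a count of dropouts and withdrawals.

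**The concern.** Membership of the analysis set is decided after treatment has started, by events that may be related to outcome. A patient withdrawn on Day 5 for a reaction, or because an interacting antibiotic was needed, has no Day 14 PDAI, is not a completer, and gives up the place to a new patient. The study is open-label with one arm, so no comparator would show the selection.

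Section 10 says the trial cannot settle efficacy, but section 8 makes it a basis for later studies and their sample size. A response rate that is too high would carry into that planning.

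Where sections 5 and 8 differ, unblinded staff could be deciding inclusion patient by patient after outcomes are known.

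**Working it through.** **The plan's own figure.** Section 8 gives no effect size, standard deviation or power, only significance at the 1% level in a paired non-parametric comparison. If every patient improves, the smallest exact two-sided p is 2/2^n: 0.0156 at n = 7, 0.0078 at n = 8, 0.0039 at n = 9. With n = 9 the signed-rank test can still absorb one adverse lowest rank (p = 0.0078); with n = 8 it cannot (0.0156). So 9 is reproducible, and 9/(1 − 0.25) = 12. The sample size is not the error.

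**Three of 12 stop, no replacement.** Inputs: 12 treated and 3 losses (section 8). Assumption: 6 of 9 completers respond (PDAI decrease of at least 3 points). Let k be the number of the three stoppers who would have counted as responders. The completer rate is 6/9 = 67% (exact 95% CI 30–93%). The all-treated rate is (6 + k)/12:

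| k | All treated | Exact 95% CI | Completer rate of 67% is |
|---|---|---|---|
| 0 | 6/12 = 50% | 21–79% | too high |
| 1 | 7/12 = 58% | 28–85% | too high |
| 2 | 8/12 = 67% | 35–90% | equal |
| 3 | 9/12 = 75% | 43–95% | too low |

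If all 9 completers respond, the completer rate is 100% (66–100%), against 9/12 = 75% (43–95%) up to 12/12 = 100% (74–100%) in all treated.

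**Replacement until 12 complete, same 25% loss.** Treated: 12/0.75 = 16. Assume 8 of 12 completers respond: 67% (35–90%). All treated: from 8/16 = 50% (25–75%) to 12/16 = 75% (48–93%).

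**Expected size if only non-responders stop.** With true response rate p, all responders completing and a share q of non-responders not completing, the completer rate is p/(p + (1 − p)(1 − q)). For an assumed p = 40%:

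- q = 10%: 0.4/0.94 = 42.6%
- q = 25%: 0.4/0.85 = 47.1%
- q = 40%: 0.4/0.76 = 52.6%
- q = 50%: 0.4/0.70 = 57.1%

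**The sections side by side.**

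| Question | Section 5, Reasons for withdrawal | Section 8 |
|---|---|---|
| Data of a withdrawn patient | Collected data stay in the final analysis unless deletion is requested | Patient excluded from the trial if missing data prevent completer status |
| Who is replaced | Patients without a second endoscopy | Anyone whose missing data prevent completer status |

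Take a Phase II patient with the Day 14 visit, examination and endoscopy but no Day 14 blood draw. The completer definition requires the bloods, so section 8 excludes and replaces this patient, while section 5 does not call for replacement. The PDAI in Appendix 1 consists of symptoms, temperature, endoscopy and histology and uses no blood test. A full primary outcome could thus be dropped for a value that the outcome does not need.

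**The case against.** Several points on the other side stand in whole or part.

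- Section 8 says completers will be included, not that only they will be. The restriction comes from the exclusion sentence, whose trigger is missing data. A patient who misses a dose but attends Day 14 in full is not clearly excluded.
- A reader might infer that sections 5 and 8 cannot both be followed. That is too strong. Exclusion from the trial can mean discontinued and replaced with earlier data kept, and section 5 does not say that only patients without the second endoscopy are replaced. The sections are misaligned, not irreconcilable.
- The last-known-value sentence need not clash with the exclusion sentence: one can cover a single missing result, the other bloods never drawn.
- A reader might infer that treatment failures are removed as such. Lack of efficacy is not a listed withdrawal reason, the window is 14 days, dosing is in hospital, and everyone receives standard antibiotics after the Day 14 endoscopy. The routes through adverse events and antibiotics are nevertheless written into section 5.
- A reader might infer that 12 is undefined, since losses are both allowed for and replaced. The summary and section 4 speak of treating 12 patients, which leans towards treated.
- A reader might infer lost significance: an exact sign test gives p = 0.0039 for 9/9 and 0.146 for 9/12. That contrast requires scoring stoppers as worsened, and the protocol names no sign test.

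The dropout count, documented reasons where given, and safety follow-up give transparency. They do not put the missing patients back into the PDAI result. An SAP, not available here, might define the set, but the protocol's stated rule would remain.

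**Conclusion.** The point holds in this form: section 8 as written can leave treated patients who do badly before Day 14 out of the Phase II PDAI result and fill their places. The bias is probably, not certainly, in the drug's favour, and its size cannot be known from the protocol. The 67% against 50% to 75% rests on the protocol's allowance of 3 in 12, which is a planning margin and not a forecast, and on an assumed 6 of 9 responders; the completer interval of 30–93% covers that whole range. What matters is that the rule makes inclusion depend on post-treatment events and that sections 5 and 8 describe inclusion and replacement differently.

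The form of the Day 1 application is a separate minor matter. The Phase II schedule in section 4 has a spray on Day 1 and enemas on Days 2–7, so six enemas. The completer definition has seven daily enemas, and section 6 (Dosage, preparation and administration), section 7 (Intervention) and Appendix 2 also describe enema use. A reader might infer that nobody treated under section 4 could be a completer; that literal reading is implausible, but the passages must be reconciled.

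**What to change.** - Make all patients who received study drug the primary set for Phase II PDAI response (decrease of 3 points or more). Count those who stop for an adverse event or reaction, or start antibiotics, before the Day 14 assessment as non-responders. Show best and worst case for other withdrawals.
- Section 8 plans and sizes a paired comparison. Present it in patients with both scores, labelled as such, with the number of treated patients not included.
- Keep completers as a sensitivity analysis.
- Do not exclude a patient with a Day 14 PDAI because a laboratory value is missing.
- Report safety in everyone who received any study drug, including replaced patients. This matters in Phase I too, where a patient withdrawn for a reaction before Day 7 is not a completer although adverse reactions are the primary outcome.
- State that replacement adds patients and removes none, and align sections 5 and 8 on whose data are analysed and who is replaced.
- Separately, reconcile sections 4, 5, 6 and 7 and Appendix 2 on the Day 1 application.

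Cost: a protocol amendment and possibly a less favourable response rate. No added visits; section 5 already permits use of withdrawn patients' collected data unless they ask for deletion.

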##### Laboratory evaluations

The following blood sample analyses will be taken to monitor signs of inflammation as well as adverse reactions to the medication.

Type of vial:	Clinical biochemistry test:	Amount of samples
EDTA	Hemoglobin; B Leukocytes; B Thrombocytes; B Leukocyte type;	2 blood samples per patient taken at baseline (Day 1) and 7 days after end of treatment
Heparin	Creatinine; P Potassium; P HCG (in females); P Alkaline phosphatase; P	2 blood samples per patient taken at baseline (Day 1) and 7 days after end of treatment
Li-Heparin	Sodium; P Bilirubin; P ALAT; P Amylase; P Lactate dehydrogenase; P	2 blood samples per patient taken at baseline (Day 1) and 7 days after end of treatment

	CRP; P	
--	--------	--

Blood samples will be analyzed by the clinical biochemistry department at the Sjælland University Hospital Køge. Per vial between 7-10 ml of blood are drawn, with 3 vials drawn both at baseline (Day 0) and 7 days after treatment. In total 6 vials of blood are drawn, with a maximum of 60 ml of blood.

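### With one blood draw before and one after treatment, carrying the last known value forward turns a missing follow-up laboratory result into zero change

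*Protocol*

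**What the plan says.** Section 8 (Statistical considerations) has two rules for missing data.

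- If the gap means that a patient is no longer a completed test person, "the patient is excluded from the trial and a new patient will be recruited".
- For anything smaller, "If individual results are missing (e.g. laboratory values), the last known values will be used for analysis".

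Section 5 defines the completed test person. In both phases the follow-up blood must have been taken; for Phase II the wording is "when new blood samples were drawn, and clinical examination and control endoscopy performed".

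Section 7 (Laboratory evaluations) schedules "2 blood samples per patient taken at baseline (Day 1) and 7 days after end of treatment" and gives the total: "In total 6 vials of blood are drawn, with a maximum of 60 ml of blood". The tests "will be taken to monitor signs of inflammation as well as adverse reactions to the medication". In section 3 the laboratory outcome is secondary in both phases and is a before-to-after comparison: "Change in median WBC, CRP, creatinine and liver enzymes from before application of the study drug". For the summary statistic, section 8 says "Differences pre- and post-treatment will be described by means and standard deviations, or median and range when appropriate".

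**The concern.** Carrying a value forward needs an earlier on-treatment or post-treatment measurement to carry. Here the only scheduled earlier value is the pre-treatment one. Used on a follow-up result, the rule therefore assumes that the patient did not change, and change is the quantity being estimated. The bias has a known direction, towards no change.

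For WBC and CRP this dilutes any effect. For creatinine and liver enzymes, which are drawn partly to detect harm, a result that nobody has seen is summarised as stable. With 6 and 12 patients, a single invented zero carries visible weight.

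**Working it through.** **1. How many draws are there?** Three vials at each of two time points give 3 × 2 = 6 vials, and at 10 ml each at most 6 × 10 = 60 ml. Both match the protocol's totals. Appendix 2 also marks chemistry and haematology once before treatment and once at follow-up (Day 7 in Phase I, Day 14 in Phase II). It places the first draw at Day 0, where the laboratory table says Day 1, but either way there is one.

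**2. Whom does the rule reach?** A patient with no follow-up draw is not a completed test person and is replaced, so nothing is carried forward. The rule applies to a completed patient whose blood was drawn but who has no result for a given analyte.

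**3. What is carried?** The last scheduled value is the baseline, so change = post − pre = pre − pre = 0. The exception is an unscheduled value, or one in the patient file, that is later than baseline. Sections 7 (Enrollment meeting) and 9 (Data from patients' files) allow access to such data.

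**4. Effect on the mean change.** Suppose f of n follow-up results are missing and those patients would have had the same mean change as the others. The mean is then multiplied by (n − f)/n. The protocol gives no missing rate, so f is assumed:

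- 1 of 12: 11/12 = 0.917, a shrinkage of 8%
- 2 of 12: 10/12 = 0.833, a shrinkage of 17%
- 1 of 6: 5/6 = 0.833, a shrinkage of 17%

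**5. Effect on medians.** The outcome is worded as a change in median, so medians were simulated with 200,000 trials per setting. The assumptions were pre ~ N(0, 1) and post = d + 0.5·pre + √0.75·e with e ~ N(0, 1). This gives a pre-post correlation of 0.5 and an SD of change of √(1 + 1 − 2 × 0.5) = 1. Then f post values were replaced by pre. The entries are the ratio of carry-forward to observed pairs for d = 0.5 / 1 / 2.

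| Missing | Difference of group medians | Median of individual changes |
|---|---|---|
| 1 of 12 | 0.919 / 0.928 / 0.947 | 0.822 / 0.889 / 0.944 |
| 2 of 12 | 0.838 / 0.850 / 0.886 | 0.630 / 0.757 / 0.875 |
| 1 of 6 | 0.836 / 0.850 / 0.887 | 0.718 / 0.780 / 0.876 |

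The difference of group medians thus shrinks by 5-8%, 11-16% and 11-16%. The median of individual changes shrinks by 6-18%, 13-37% and 12-28%.

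**6. Does carry-forward buy anything?** Power of a two-sided 5% paired t-test, observed pairs v carry-forward:

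| Missing | d = 0.5 | d = 1 |
|---|---|---|
| 1 of 12 | 0.323 v 0.320 | 0.848 v 0.846 |
| 2 of 12 | 0.292 v 0.286 | 0.803 v 0.797 |
| 1 of 6 | 0.140 v 0.123 | 0.402 v 0.364 |

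Power with carry-forward is lower in every row. A Wilcoxon signed-rank test that drops zero differences gives the same p-value either way.

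**The case against.** The strongest reply is that the reach is narrow and the effect small. Patients without a follow-up draw are already replaced, the samples go to a hospital biochemistry department, and nothing in the protocol suggests that single analytes will often be missing. With 1 of 12 missing and a true shift of 1 SD, the mean moves by 1/12 ≈ 0.08 SD, against a standard error of 1/√12 ≈ 0.29 SD. The loss of power is slight except at 1 of 6, and that is Phase I, whose purpose is tolerability. Shrinkage is also conservative for WBC and CRP in an uncontrolled study. An abnormal laboratory finding counts as an adverse event in its own right, and section 8 provides for continuous evaluation of adverse reactions.

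Most of this stands as a limit on size. The largest percentages belong to the median of individual changes, whereas the outcome wording reads more naturally as a difference of group medians, where 1 of 12 costs 5-8%. The argument does not rescue the rule. The narrow case is the one the sentence was written for, and there it normally inserts a zero. Conservatism does not apply to creatinine and liver enzymes, where no change is the reassuring answer. Adverse-event recording is unaffected, but it does not correct the laboratory summary.

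A further point is fair: the calculations cover laboratory-type data only. The rule's wording is not confined to laboratory values and could reach a missing PDAI component, for example a histology subscore, which contributes to the Phase II primary outcome. No size was worked out for that case.

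**Conclusion.** The point holds. As written, the rule sets a missing follow-up laboratory result equal to baseline by default and analyses it as no change. Nothing happens if nothing is missing. With one or two results missing, the mean change shrinks by 8% to 17% and the difference of group medians by 5% to 16%, with no gain in power to set against the bias.

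The mean figures assume that the missing patients resemble the rest. The median and power figures also assume normal data and a correlation of 0.5, with true shifts of 0.5 to 2 SD for the medians and 0.5 and 1 SD for power. The missing counts are assumptions throughout. The demonstrated effect is on secondary laboratory outcomes and touches neither adverse-event recording nor the Phase I primary outcome. The rule should be changed, but it does not threaten the trial.

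**What to change.** In section 8, replace the carry-forward sentence with:

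> If an individual laboratory result is missing, the change in that variable is analysed in patients with both a pre- and a post-treatment value. No baseline value is substituted for a missing post-treatment result, and the number missing is reported for each variable.

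Because the present wording is not limited to laboratory values, add that a baseline PDAI subscore is not carried forward either, and state how the PDAI total is handled when a subscore is missing.

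The cost is a sentence or two of text. Some laboratory variables may have one or two fewer pairs, with no loss of paired-test power compared with carry-forward in the settings examined. No visit, sample or patient number changes.
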